COVID-19 by either study or clinical testing will complete the study at that timepoint. Every effort to obtain confirmatory test results for COVID-19 will be done, including patient self-report, at study evaluations if presenting with symptoms, and from supportive medical records or study testing. At this point, participants having been diagnosed with COVID-19 will be asked if they would be willing, within 30 days of recovery, to present for a study visit to provide a blood sample and answer an end of study questionnaire than can be scheduled at a later time. All participants will be monitored for safety 30 days post study completion.

Any potential study Participant who screens positive for COVID-19 symptoms or tests positive for SARS-CoV 2 during screening or subsequently during the trial, will be referred to their respective providers for further testing and care. HFHS employees will be directly referred to employee health for further evaluation.

Study questionnaires will obtain information on Participant demographics, clinical background, clinical symptoms, employment, work activities, location of main work area, known possible exposures to COVID-19 patients, potential medication side effects and adherence to study treatment regimens. Complete questionnaires are located in the appendix section.

Additional laboratory studies will include plasma serologies, cellular & systemic inflammatory markers as well as other disease associated markers. Samples will be stored for future studies as new markers of SARS-COV-2 infection and COVID-19 disease may be yet to be identified.

Samples will also be stored for potential future HCQ level testing. The testing will be done for samples from both randomized treatment arms and comparator arm subset of patients to assess their study compliance as compared to the medication adherence indicated in the study questionnaires. HCQ drug levels will provide further information regarding drug levels and their association with the effectiveness of the treatment strategies on prevention of symptom development and clinical & laboratory confirmed disease.

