All collected specimens will be sent directly to the research laboratory for processing, analyses and storage. Patients who develop clinical symptoms for SARS-CoV-2 will have both clinical referral for testing and study blood collected. Additional testing for serology, immunology and other markers will be done later in the study. Samples will be stored in appropriately monitored – 80°C freezers or liquid nitrogen containers in the Division of Infectious Diseases and/or Translational and Clinical Research Center laboratories for testing.

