### **7.3 SAMPLE COLLECTION AND HANDLING**

Five (5) 10 ml blood tubes consisting of 4 EDTA and 1 Shield tubes of whole blood will be collected from each participant at the baseline/enrollment, week 4 and week 8 timepoints. The samples will be collected using standard aseptic procedures and will be stored in a 4°C refrigerator or cooler until transport to the research laboratory where the samples will be processed. Samples will be processed to serum plasma or cell components. Testing for SARS-CoV 2 will be done for study entry samples. Remainder of the samples will be stored in -80°C for whole blood/serum plasma and cell samples will be stored in liquid nitrogen for future testing.

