## 9 PARTICIPANT INVOLVEMENT ENDPOINT/FOLLOW-UP

All Participants who sign the Consent and Authorization Form and provide three (3) blood sample draws, complete the baseline and week 1- 8 assessments, or after acquiring COVID-19 infection at any point during the study period are considered to have completed participation in this study. Participants will be followed for 30 days after meeting study endpoint for safety purposes. No further follow-up by the study Investigator is planned for Participants involved in this study thereafter. Electronic medical records will be accessed to obtain information on any diagnostic testing done for COVID-19 as part of the Participants’ routine care which may lead to diagnosis of COVID infection, including but not limited to PCR, serologies, rapid diagnostic tests, and other related tests.

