6.3 Study Aims, Hypothesis and Proposed Analysis

6.3.1 Primary Aim and Hypothesis

As noted below, the primary aim has been changed to: (based on Study Protocol dated 05/26/2020)

To determine if the use of hydroxychloroquine as preventive therapy decreases the rate of acquisition of SARS-CoV 2 infections [with clinical COVID-19 disease](#) in Study Participants [for each randomized treatment arm](#) as compared to placebo.

From: (based on original Study Protocol, dated at and after 04/06/2020)

To determine if the use of hydroxychloroquine as preventive therapy decreases the rate of acquisition of SARS-CoV 2 infections in Study Participants as compared to placebo.

Primary Hypothesis (P1): Hydroxychloroquine administered daily decreases the rate of acquisition of SARS-CoV 2 infections with clinical COVID-19 disease, compared to placebo; and hydroxychloroquine administered weekly decreases the rate of acquisition of SARS-CoV 2 infections with clinical COVID-19 disease, compared to placebo.

The **primary outcome** will be defined as clinical COVID-19 disease with laboratory confirmation of infection.

Presentation with COVID-19 symptoms during study follow-up (defined as fever $\geq 38^{\circ}$ C, or two or more non-fever symptoms that are new since the baseline) will refer participants to obtain SARS-CoV 2 testing through employee health or participants' primary care physician, with test results documented in their medical record.

Laboratory confirmation of SARS-CoV 2 infection (SARS-CoV 2 test positive) will be defined as at least one positive RT PCR, or both IgM and IgG positive serology. The lab test results can be obtained from (a) study blood samples (IgM and IgG serology), and (b) RT PCR test results ordered by a participant's primary care physician or through employee health.

All participants who test SARS-CoV 2 positive will be followed for at least 30 days after the first positive test for presentation of symptoms.

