6.3.4. Proposed Analysis

6.3.4.1 General Statistical Consideration:

The statistical software package SAS® Version 9.4 or higher (SAS Institute, Cary, NC, USA) will be used to perform all analyses and to summarize data.

The analyses described in this statistical analysis plan (SAP) are considered a priori, in that they have been defined prior to database lock. Any analyses not described herein performed subsequent to database lock will be considered post hoc and exploratory.

6.3.4.2. Handling of missing data:

For summary statistics, results will be reported based upon observed data. The study will make all possible efforts to obtain patient's follow-up data and laboratory confirmation of infection for COVID 19 disease determination. The efficacy analysis will be performed based on all observed data assuming missing as random (MAR), two selected imputation approaches are specified for the sensitivity analysis.

6.3.4.3 Primary Efficacy Analysis.

The FAS is considered. Chi-square test will be used to compare the rate of COVID-19 disease in each randomized treatment group to that of the placebo group using Dunnett's step-up method to adjust for multiple comparisons and controlling for type I error^{1,2}. Specifically, Dunnett's step-up method uses a closed gatekeeping strategy, in which the largest p value will be evaluated first at critical value of 0.05; if that fails, the second p value will be evaluated at critical value of 0.0262 (details in the sample size /power calculation section). A treatment efficacy is detected if the largest p value <0.05 or the second p value <0.0262 . The results of

efficacy analysis will be validated through two specified imputation approaches described in below

Sensitivity Analysis #1: A Tipping Point Analysis (TPA) with delta-adjusting imputation

The primary analyses for COVID 19 disease is based on the observed data and the results are valid if the missing data are missing at random (MAR), meaning that the probability of a value being missing, conditional on the observed data and factors in the statistical model, is random and not dependent on the unknown value of the missing data point.

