To address this, we will conduct Tipping Point Analysis (TPA) under the condition of missing not at random (MNAR) to assess the robustness of the primary analysis. Specifically, the TPA first step (STEP 1) is to conduct m (e.g., $m=5$ or 10) multiple imputation (MI) based on baseline covariates, and the prior to 8-week and post-baseline covariates to estimate the missing primary binary endpoint (D) with the underlying assumption of MAR. We will use the Markov Chain Monte Carlo (MCMC) algorithm based on the assumption of multivariate normality (Schafer 1997, Allison 2001) for estimating the mean of D (Allison 2017) stratified by treatment group without rounding to binary values. However, this approach is still under the MAR assumption and hence the result will be further examined by shifting the imputed mean of D in a range of negative to positive values, which can be done by inflecting or suppressing the mean of D among those who had missing D in treated group. A tipping point is identified if it reverses the study conclusion. Those results will be further evaluated on whether the imputed value associated with the tipping point is plausible. SAS Procedures PROC MI and PROC MIANALYZE and SAS %midata macro can be used for TAP analysis.

Sensitivity Analysis #2: A control-based MI

For the most conservative approach, MI can be restricted using data only from the placebo group for the missing endpoint D in both the treated and placebo groups using a similar approach described above for the sensitivity analysis #1 with the shift=0 (the first step).

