Secondary Hypothesis (S7): There is an HCQ dose effect on AEs and SAEs, compared to placebo.

The endpoint will be any AE and any SAE observed during the 8 weeks of follow-up after enrollment.

Safety Analysis Set is considered by including all randomized subjects.

A descriptive analysis will report AE frequency and grade distribution among the three arms, and include a detailed list of serious adverse events (SAEs).

S8: To examine other clinical determinants contributing to the risk of SARS-CoV 2 infection including demographics, work type and location, positive COVID-19 partners, possible exposures and clinical symptoms.

Secondary Hypothesis (S8): Risk for SARS-CoV 2 infection varies by subject demographics, work type and location, and clinical conditions.

The possible covariates will include subject demographics, work type and location, and clinical conditions at the baseline prior to study enrollment, as well as the study treatment status. The endpoint will be clinical COVID-19 disease confirmed by laboratory test (same endpoint as P1).

FAS is considered. Logit univariate and multivariate modeling will be conducted with consideration of possible treatment-by-baseline covariate interaction. Variables will be retained in the final model if there is significant individual effect or variable-by-treatment interaction at p-value 0.05. Area under the receiver operating characteristic curve (AUROC) will be used to assess the predictive ability.

S9: To examine the association between HCQ drug levels and development of COVID-19 symptoms or positive test results.

Secondary Hypothesis (S9): There is an association between HCQ drug levels and development of COVID-19 symptoms or positive test results.

The endpoint will be the same, as described for S1 *using FAS*.

A similar analysis as that described for S1 will be used. The analysis will include concentration of HCQ in blood at baseline, week 4 and week 8 as covariates.

S10: To identify immunologic, serological and inflammatory markers associated with acquisition and response to COVID-19 in both HCQ and placebo Participants developing laboratory or clinical confirmed disease.

Secondary Hypothesis (S10): There are immunologic, serological and inflammatory markers for COVID-19 positive.

Two separate endpoints, SARS-CoV 2 test positive, and COVID19 disease with SARS-CoV 2 test positive laboratory confirmation (P1), will be considered.

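### S9 uses a week-8 HCQ level that clinically diagnosed cases either lack or have measured after the event, and the SAP has no rule for either situation

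*SAP*

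**What the plan says.** **The analysis.** S9 (SAP 6.3.4.4) takes the three-level S1 infection status in the FAS: never test-positive, test-positive without symptoms, test-positive with symptoms. It uses the S1 ordinal logistic approach and adds drug levels: "The analysis will include concentration of HCQ in blood at baseline, week 4 and week 8 as covariates".

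**Exit at diagnosis.** Under SAP 6.3.1, new symptoms during follow-up "will refer participants to obtain SARS-CoV 2 testing through employee health" or a primary care physician. Protocol section 4 says that participants found positive for "COVID-19 by either study or clinical testing will complete the study at that timepoint". Protocol section 9 agrees: those who finish all assessments "or after acquiring COVID-19 infection at any point during the study period are considered to have completed participation in this study".

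**Blood draws.** Protocol 7.3 says that samples "will be collected from each participant at the baseline/enrollment, week 4 and week 8 timepoints". The schedule in 7.2 puts the draw at a positive diagnosis in a separate column. The protocol describes post-diagnosis sampling in four ways:
- Synopsis: at week 8 or on a positive diagnosis.
- Section 4: within 30 days of recovery, if the participant is willing.
- Section 4.2: an unplanned visit after four weeks from diagnosis.
- Section 7.2, footnote c: attempted on anyone who tests or screens positive.

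**Confirmation by serology.** SAP 6.3.1 also accepts IgM and IgG both positive on study samples. Protocol section 4 places this work later: "Additional testing for serology, immunology and other markers will be done later in the study".

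**Missing data.** SAP 6.3.4.2 bases the efficacy analysis on observed data under MAR. The multiple imputation in the sensitivity analyses is there "to estimate the missing primary binary endpoint (D) with the underlying assumption of MAR". No rule covers a missing drug level.

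**The concern.** Randomised participants are not on HCQ at entry, so the information in S9 lies in the week-4 and week-8 levels. Both are drawn inside the period in which the outcome occurs. S8 and S10, the neighbouring aims, use baseline covariates and baseline blood. S9 does not.

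For a participant diagnosed clinically before week 8, the week-8 level can be handled in two ways, and neither is sound.

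- **Scheduled draws only.** The level is missing because the outcome occurred. A complete-case fit loses nearly all clinically diagnosed infections. It mainly compares serology-detected infections with non-cases, and says little about symptomatic infection, which S9 asks about by name.
- **A post-diagnosis sample stands in for week 8.** The predictor is then measured after the event it should explain, and at a different time from dosing than in non-cases. Cases and non-cases can differ in level for that reason alone.

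The documents do not choose between these, so the choice would fall to the analyst after the data are in.

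**Working it through.** The documents give no power, sample size or loss figure for S9, so there is none to reproduce.

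**Inputs from the documents.** Follow-up of 56 days, visit window of +/-3 days, draws at weeks 4 and 8, exit at a positive test, HCQ half-life of 172 hours to 50 days (Protocol 10.3).

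**Assumptions.** Diagnosis day D even over days 0-56. Week-8 draw V even over days 53-59. Complete-case fit. Both timing assumptions are varied below.

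**1. Clinically diagnosed cases with a scheduled week-8 level.** The draw must come no later than diagnosis:

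P(V <= D) = [integral from 53 to 56 of (56 - v) dv] / (6 x 56) = 4.5 / 336 = 1.3%, so 98.7% have none.

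| Variation | Without a week-8 level |
|---|---|
| Even timing, even window | 98.7% |
| Week-8 draw always on day 53: 1 - 3/56 | 94.6% |
| Diagnosis density tilted early or late by up to a factor e^2 | 97.0-99.6% |

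**2. Week-4 level also missing.** Diagnosis before day 28: 28/56 = 50%. With the same tilts, 27-73%.

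**3. All symptomatic test-positive cases.** Let s be the share confirmed only by stored-sample serology. They stay to week 8 and keep the level. Loss = (1 - s) x 98.7%:

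| s | Loss |
|---|---|
| 0% | 98.7% |
| 10% | 89% |
| 20% | 79% |
| 30% | 69% |
| 50% | 49% |

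The documents do not give s. The retained cases have a week-8 level that was drawn after infection.

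**4. Post-diagnosis draws counted when they fall in the week-8 window.** Diagnosis on days 53-56 adds 3/56. A draw four weeks after diagnosis falls on days 53-59 if diagnosis was on days 25-31, which adds 6/56. Kept: 9/56 = 16%, so 84% are still lost, and the levels gained are post-event.

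**5. Any post-diagnosis sample used as week 8.** Assume dosing stops at diagnosis, first-order elimination, and a draw 28 days later. The fraction of the diagnosis-time level that remains is:
- half-life 172 h: 2^-(672/172) = 2^-3.91 = 7%
- half-life 50 days: 2^-(28/50) = 2^-0.56 = 68%

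Non-cases are still dosed up to week 8. Cases therefore show lower levels with no drug effect, which looks like protection. For a sample taken at diagnosis, the size and sign depend on half-life, dose phase and model.

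**6. Simulated illustration.** 1000 trials per setting. Assumed: HCQ arms only, 900 per arm, 10% infected (180), half of them diagnosed clinically, every symptomatic case diagnosed clinically, between-person CV 40%, sample noise 15%.
- *Scheduled draws, complete cases.* False positives stay at 5-6%. If higher levels reduce only symptomatic infection (odds ratio 0.5 per SD of log level), power is about 5%. A week-4 level with later symptomatic infection as outcome gives 99%. If levels act on all infections (odds ratio 0.7, 50-day half-life), the gap is small: 83% against 88% for the week-4 level with S1 status as outcome.
- *Recovery sample as week 8, no drug effect.* False positives are 100% if dosing stopped at diagnosis and 77-100% if it continued. With 15% diagnosed clinically they are 63-99.6% and 13-93%.

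**The case against.** The strongest reply is that S9 does not say what is being criticised. Analysing observed data under MAR is not a deletion rule for covariates, and S9 does not say that all three levels must enter one complete-case model. The synopsis pairs week 8 with a positive diagnosis, so reading the diagnosis draw as the end-of-study sample is natural. SAP 6.3.1 follows positives for at least 30 days, and S6 also looks beyond diagnosis. The SAP cites a protocol dated 05/26/2020, which may be later than the one supplied. S9 is ninth of ten secondary aims, and protocol section 4 describes level testing as potential future work, possibly in a subset.

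Much of this stands. The loss figures are conditional, and the post-diagnosis reading is open. But that reading puts the predictor after the event, and the extended follow-up in the SAP schedules no blood draw. Neither route gives a sound week-8 predictor for these cases.

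Two stronger readings are tempting, and the documents do not support them.

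- **That about 99% of symptomatic cases are lost.** That figure belongs to clinically diagnosed cases. The symptomatic category in S1 also admits serology confirmation, and those participants reach week 8.
- **That S9 has a known low power or would report harm.** A wrong-direction result can arise if higher levels only make infections milder, but its frequency depends on s. In a simplified check (half of infections symptomatic, odds ratio 0.5), significant harm fell from 79% of trials at s = 0 to 35% at s = 30% and 16% at s = 50%. The simulations also leave out placebo, which the FAS includes, and assume 10% infected in the HCQ arms. The SAP plans 6.8% clinical disease there, about 122 cases in 1800.

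**Conclusion.** The point holds in a limited form. S9 uses levels from within the outcome period, positive participants complete the study at diagnosis, and no rule covers the missing level. The week-8 level of a clinically diagnosed case is therefore either missing because of the outcome or drawn after it.

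With scheduled draws only and a complete-case fit, about 95-99% of clinically diagnosed cases lack a week-8 level and about half also lack a week-4 level. Among all symptomatic cases the loss is roughly 49-89% for s between 50% and 10%. These figures rest on the timing assumptions and on s, which the documents do not give. The simulated rates are illustrations, not properties of the plan.

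A reader might infer that the trial's efficacy conclusion is at risk. It is not: the primary analysis uses no drug levels. This should be corrected before S9 is run.

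**What to change.** State in S9 that only HCQ levels drawn before the first positive test and before symptom onset are predictors. One workable form:

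- **Population:** HCQ-arm FAS participants who are symptom-free and test-negative at week 4, including IgM/IgG on the stored week-4 sample.
- **Predictor:** log week-4 level.
- **Outcomes after week 4:** (a) S1 status; (b) symptomatic test-positive against all others. Both adjusted for arm and risk stratum. Outcome (b) is needed because, if levels only make infections milder, the ordinal model has about 5% power in the simulation, against 47-50% for (b) at odds ratio 0.5.
- **Descriptive only:** week-8 levels of earlier cases and all diagnosis-time and recovery samples.
- **Missing levels:** counted by arm and outcome.

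The last pre-event level, with non-cases matched on study day, is an acceptable alternative.

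The protocol synopsis and sections 4, 4.2 and 7.2 should be reconciled on when the post-diagnosis sample is drawn, in the protocol version that the SAP cites.

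**Cost.** SAP wording and the same blood samples, plus serology on stored week-4 samples if not already planned. Infections before week 4 do not contribute, about half under even timing. With 180 infections the landmark keeps about 90. The complete-case fit keeps about 91 if half are diagnosed clinically (90 + 1.2) and 153 if 15% are (153 + 0.4), but almost none of those are clinically diagnosed. A participant infected just before week 4 may still be seronegative and count as a later case. This blurs timing but does not alter the week-4 level.

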6.4 Sample size/power calculation

Power Calculation for original Primary Aim: (based on original Study Protocol, dated 04/06/2020)

To determine if the use of hydroxychloroquine as preventive therapy decreases the rate of acquisition of SARS-CoV 2 infections in Study Participants as compared to placebo.

The sample size and power calculation for the original aim are based on a SARS-CoV 2 infection rate of 10% in the placebo-treated group, and an average of 6.8% in the randomized weekly- and daily- HCQ groups, with a relative reduction of 32%. Based on an alpha=0.05 two-sided test, with 900 subjects per group that are COVID negative at the baseline, and one interim analysis when 50% of participants (450 per group) have completed the study and primary

endpoint data assessment, we will have more than 80% power (82% to be exact using nQuery) to detect a significant HCQ effect if the observed test statistic is ± 2.9626 or $p\text{-value} < 0.003$ in the interim analysis, or ± 1.9685 or $p\text{-value} < 0.0497$ in the final analysis, using an O'Brien-Fleming alpha spending method to ensure an overall type 1 error of 0.05 and assuming that overall COVID positive rate in the weekly- and daily- dose HCQ groups is 6.8% with $n=1800$ in the HCQ treated group and 900 in the placebo treated group. A reduction of 36% can be detected between either one of the HCQ treatment groups and placebo, using the same assumptions. Assuming 5-10% of patients will have SARS-CoV 2 positive at the baseline, we need 1000 per group, with a total of 3000 participants to complete the trial.

Power Calculation for revised Primary Aim: (based on revised Study Protocol dated 04/16/2020 or after)

To determine if the use of hydroxychloroquine as preventive therapy decreases the rate of acquisition of SARS-CoV 2 infections with clinical COVID-19 disease in Study Participants for each randomized treatment arm as compared to placebo.

The revised sample size and power calculation are based on a 10% rate of clinical COVID-19 disease (with laboratory confirmation) in the placebo-treated group, and an average 6.8% rate in the two randomized HCQ-treated groups (weekly and daily dosing groups), with a relative reduction of 32%. We propose two looks; one look (interim analysis) when 50% of the participants have completed the study and primary endpoint assessment (for P1), and a final look when 100% of participants have completed the study.

Based on an $\alpha=0.05$ two-sided test, chi-square test/logistic regression with odds ratio estimates, and Haybittle-Peto alpha spending method to ensure an overall type I error, the critical value for the interim analysis will be 0.001 and the critical value for the final analysis will be 0.05. For data illustration, we have also included an O'Brien-Fleming spending function approach for controlling type I error with a critical value of 0.0054 for the interim analysis and 0.0492 for the final analysis.

Power calculations are based on $n=900$ or 935 participants per study arm, using a simulation approach ($n=10,000$ simulations) in three correction methods: #1 comparing the weekly and daily HCQ dose arms to the placebo group separately using the Dunnett's step-up approach; #2 comparing the weekly and daily HCQ dose arms to placebo separately using a conservative Bonferroni approach with critical value of 0.025 for each test at the final look; #3 comparing the combined weekly and daily HCQ dose arms to the placebo using a single test.

With Haybittle-Peto boundary and $\alpha=0.05$ at the final look, the Dunnett's step-up correction uses a closed gatekeeping strategy for testing the daily dose arm vs placebo and the weekly dose arm vs placebo separately: the largest p value tested first will be at 0.05; if that fails, the second test will be at p value 0.026, delivered from the last row of Table 2 of Dunnett and Tamhane (1992), and validated based on simulation using R *DunnettTests* package. Likewise, at the interim look, the largest p value tested first will be at 0.001; if that fails, the second test will be at 0.0005.

Table 1. Power for different scenarios using varying methods. Sample size was determined using the Dunnett's Step up method with the Haybittle-Peto boundary.

Haybittle-Peto approach	$p_0=0.1, p_1=0.073, p_2=0.063$		$p_0=0.1, p_1=p_2=0.068$	
Method	n=900	n=935	n=900	n=935
#1 Dunnett's Step up	0.800	0.811	0.770	0.800
#2 Bonferroni	0.784	0.800	0.745	0.760
#3 Daily+weekly arms vs placebo	0.812	0.83	0.819	0.835

p_0 is the rate for the placebo treated group and p_1 and p_2 are the rates for the two treated groups.

O'Brien-Fleming approach	$p_0=0.1, p_1=0.073, p_2=0.063$		$p_0=0.1, p_1=p_2=0.068$		
Method	n=910	n=935	n=900	n=935	n=970
#1 Dunnett's Step up	0.8	0.814	0.76	0.776	0.801
#2 Bonferroni	0.787	0.8	0.741	0.761	0.784
#3 Daily+weekly arms vs placebo	0.815	0.83	0.815	0.83	0.846

p_0 is the rate for the placebo treated group and p_1 and p_2 are the rates for the two treated groups.

For the primary Aim / hypothesis, we will use Dunnett's Step up approach to test each dose effect vs. placebo, and a sample size of 935 per arm will insure at least 80% power. The power will be higher for some of the secondary Aims (S1-S4 if use the compressed binary endpoint of infection presence or absence), since a single test will be used to study overall dose effect first, followed by subgroup analysis (Correction Method #3)

Assuming 5-10% of patients will be excluded from FAS, we need 1000 subjects per group, with a total of 3000 participants to complete the trial. The power and sample size calculation remained unchanged.

